### **5.2 Recruitment Methods**

**Description of the Recruitment Process:** Recruitment will be based on convenience sampling using available participants from Madigan/JBLM and VA Puget Sound. We anticipate enrollment of 228 participants to achieve 160 randomized -- an average of approximately 4-5 participants randomized per month divided approximately equally across the 2 sites.

At VA Puget Sound, participants will be recruited via referrals from VA outpatient clinics, including Neurology, Primary Care, Mental Health, Neuropsychology, Rehabilitation Medicine, Deployment Health, Polytrauma, and others; periodic, informational e-mail to providers and clinics summarizing the study, eligibility criteria, study PI, study staff contact information, and instructions for proper referral of potentially eligible participants; VA community-based outpatient clinics (CBOCs); local area Veterans centers; National Guard and Reserve units; hospital health fair and hallway information tables; public outreach presentations; posted IRB-approved advertising in highly trafficked areas **and** clinic waiting rooms; advertisements in newsletters, local newspapers, radio, and the Internet (including social media); presentations to appropriate clinical services (such as grand rounds presentations or service staff meetings); e-mail and presentations to local non-VA providers and community groups (e.g., TBI support groups); and word-of-mouth.

Similar recruitment strategies will be employed at Madigan/JBLM on and off-site facilities, with the addition of the TBI Program, the Warrior Transition Battalion, educational outreach to the brigades, JBLM Family & Morale, Welfare & Recreation Facilities, JBLM Education Center and a large banner at the gates into JBLM.

Interested potential participants will contact the study team for more information. The study will be described privately either over the telephone, via VA or DoD approved telehealth applications, or in person; eligibility requirements will be explained, preliminary eligibility will be determined, and any questions will be addressed. Those meeting initial eligibility criteria will be scheduled - SMs and Tricare-eligible Veterans who receive care at Madigan will be seen at Madigan and Veterans who are eligible for care through the VA will be seen at VA Puget Sound for an initial screening visit. Written study information and consent forms will be sent to potential participants for their review prior to that visit whenever scheduling time allows.

#### **Compensation:**

Veteran participants (at VA Puget Sound and Madigan sites) will be compensated \$100 for each of 2 weeks of actigraphy monitoring and \$50 per in-person study visit to defray transportation costs and inconvenience, up to a total of \$950. In addition, participants may receive a blood pressure cuff to use for remote visits that require an orthostatic vital signs assessment, which participants will keep at the conclusion of their participation. Veterans will be compensated for extra study visits that may be required per clinician judgement (i.e., extra safety visits or extra titration visits). Payments will be prorated, based on the number of completed study visits and weeks of actigraphy. In addition, Veteran participants will be compensated an additional \$25 per visit if they must travel between 50-100 miles round trip and \$50 per visit if they must travel over 100 miles round trip to attend study visits, to defray travel costs.

For visits done remotely (by telephone or telehealth), Veterans will be compensated according to the guidelines below, based on the level of burden placed on the participant per visit:

- Participants will not be paid for the telephone safety checks, such as P1.5, P2.5, and SD3.5 visits.
- For lower-burden visits, such as the P2, P3, T2-T8, and SD1 visits, participants will receive \$20 per remote visit
- For higher-burden visits, such as the P1, T1, and SD2-SD4 visits, participants will receive \$50 per remote visit.

This rate of compensation complies with the VA Puget Sound IRB guidelines for prevention of research study participant financial coercion.

Active-duty and Federal Personnel participants at Madigan: Per Section 30 of Title 24, U.S.C.:

- Active-duty SMs and Federal personnel cannot be reimbursed for any of the study procedures, except for \$50 compensation if a blood draw is performed. In this study, Madigan participants may have one blood draw if laboratory evaluations are clinically indicated.
- SMs and Federal personnel while off duty may be compensated for research participation other than blood draws in the same way as human subjects who are not Federal personnel. If a Madigan participant is off duty while completing study procedures, they will be compensated as detailed for VA Puget Sound participants above.

All payments will occur through one of the foundations overseeing the grant. No payments will be made directly by a government source.

#### **5.3 Informed Consent Procedures**

We will be performing a Medical Records Review before obtaining written study consent as follows: potential participants will contact the study team as described above, or may be referred to the study by their health care provider (the provider would either obtain permission from his/her patient to release the potential subject's name and contact information to the study team, or the provider will give the study team's contact information to the potential participant). After the potential participant has spoken to a member of the study team and given verbal permission to have medical records reviewed, a trained study team member will review the records to screen for exclusionary medical conditions and medications. We will first obtain a waiver of the requirement to obtain Health Insurance Portability and Accountability Act of 1996 (HIPAA) authorization and consent in order to pre-screen medical records from the VA Electronic Health Record (EHR) system or the Madigan EHR system. If we require non-VA/Madigan (i.e., private medical provider) records, a written Release of Information (ROI) will be obtained.

If the potential participant remains eligible following initial chart review, an appointment will be scheduled for the Consent and Preliminary Screening Visit. The written informed consent process will take place prior to performing any study procedures.

**Personnel who will be obtaining Informed Consent:** Before study staff are considered qualified to obtain consent, they must first undergo all VA and/or Madigan-mandated trainings and will also undergo internal training. They must become familiarized with MIRECC procedures regarding obtaining consent, must be familiar with the study protocol, and must be familiar with the risks and benefits of study participation. Once the PI is satisfied that a study staff member is competent to obtain consent, he will formally delegate authority to obtain consent to that person. Because this is a clinical trial, a clinician (physician, physician assistant, or nurse) will be available either in person or by telephone to answer any of the potential participant's questions regarding the study drug.

**Description of the Informed Consent Process:** The PI or another qualified study staff member will explain the consent form at the first visit before study procedures are performed. If an investigator is also one of the potential participant's care providers, an alternate study staff member will conduct the consent process. Any pressure or appearance of pressure to participate in the study will be carefully avoided. No person in a SM's direct chain of command shall be present during the consenting process. The consent discussion will be conducted in a private location. If the potential participant wishes to have a relative or friend present during the consent process, we will accommodate the potential participant. The person obtaining consent will give the potential participant adequate time to read the consent form and ask questions. The following elements will be discussed with the potential participant:

• The purpose and objectives of the study

- The length of the study
- Any potential risks, discomfort and inconvenience
- The importance of following study procedures
- The importance of compliance with all assessments and study visits
- The possibility of the need for unscheduled visits
- Randomization there is a 2-1 chance of being randomized to either prazosin or placebo
- Participation is entirely voluntary and that the subject may withdraw from the study at any time without loss of benefits to which he/she may otherwise be entitled
- Alternative treatments
- Compensation schedule for visits
- The participant's social security number (SSN) is required in order to maintain a medical record and to reimburse participants. Participants will be informed that if they do not wish to give us their SSN, they cannot participate in the study.
- Provisions for keeping study data confidential and exceptions to confidentiality
- That adverse events are treated at no cost to the participant

The participant must sign an informed consent and HIPAA authorization as approved by the appropriate (Madigan or VA Puget Sound) IRB before any study procedures are performed. A progress note will be written in the participant's study chart to document that the consent discussion was conducted and all questions were answered to the participant's satisfaction. A note will also be placed in the EHR of participants at VA Puget Sound per current guidelines.

If the safety of a potential participant would prevent the participant from travelling to the study clinic location, initial consent may be obtained over approved VA or DoD telehealth applications. Telehealth consenting will be done according to the following steps:

- 1) All appropriate consent and HIPAA document(s) will be sent to participants via mail or secure email (e.g., Azure RMS) for the participant to print.
- 2) Participants will be given as much time as desired to review the document(s) prior to the consent discussion.
- 3) A qualified study team member will review all elements of the consent and HIPAA document(s) with the participant.
- 4) If signed, the study team member will take a screenshot of the signature page(s) of all signed study documents. The screenshot(s) will be saved in an approved, secure study folder.
- 5) The study team member will document the consenting process and enroll the participant in the study.
- 6) Participants will mail the signed document(s) to the study team using a provided pre-paid envelope.
- 7) Once the signed documents are obtained by the study team, the documents will be retained according to policy.

If an error in the signing process or documents is discovered, the error will be corrected and properly documented prior to any further study procedures.

A copy of the informed consent form can be provided to interested potential participants to review and discuss with family members or their medical provider without any time limit.

All participants will be able to provide consent on their own behalf. Because all assessments are conducted in English, all subjects will be sufficiently fluent in English to read and understand the consent form. We do not anticipate enrolling any illiterate volunteers.

VA Puget Sound IRB 2 Effective Date: Nov

November 12, 2021

## 5.4 Inclusion/Exclusion Criteria

#### **Inclusion Criteria:**

- Male and female Active-duty SMs or Veterans aged 18 or older who are in good general health.
- History of blast and/or impact head trauma mTBI meeting Defense and Veterans Brain Injury Center (DVBIC) mTBI criteria.
  - Mild TBI is defined as an injury to the head causing at least one of the following: alteration in consciousness (for up to 24 hours after the injury), loss of consciousness (0-30 minutes), and/or post-traumatic amnesia (up to 1 day post-injury). If available, the Glasgow Coma Scale score must be 13-15, and head imaging findings (if imaging was performed) must be negative.
- Frequent HAs that started within 3 months after a head injury or marked worsening (a two-fold or greater increase in frequency and/or severity) of pre-existing headaches within 3 months of head injury.
  - HAs either 1) must last 4 or more hours a day and reach a moderate to severe intensity at any point during the headache, or 2) may be of any severity or duration if the participant takes a medication or other agent in an effort to stop or treat a headache.
  - HAs meeting these criteria must have been present on average at least 8 days per 4-week period, starting within 3 months after head injury and occurring at a stable level by self-report for at least 3 months prior to the Initial Screening Visit. The 4-week HA frequency/severity criteria must be confirmed during the Preliminary Screening Period.
- Participants of childbearing potential must agree to abstain from sexual relations that could result in pregnancy or use an effective method of birth control acceptable to both participant and the clinician prescriber during the study. Participants who not of childbearing potential are not required to use contraception during the study.
- Participants must have English fluency sufficient to complete study measures.

#### **Exclusion Criteria:**

- Participation in other interventional research.
- History of penetrating head injury
- History of TBI more severe than mild by DVBIC criteria
- A primary non migraine and/or tension-type HA disorder (for example hemicrania continua; cluster) that accounts for the majority of current symptoms.
- HAs of any kind of moderate or severe intensity on an average of more than 4 days per month preceding the concussive trauma
- Acute or serious medical illness or unstable chronic medical illness (e.g., unstable angina, myocardial infarction within 6 months, congestive heart failure, clinically significant or concerning cardiac arrhythmias; preexisting hypotension [systolic blood pressure<110] or orthostatic hypotension [systolic drop >20 mm Hg after 2 min standing accompanied by lightheadedness], chronic renal or hepatic failure, or acute pancreatitis. The eligibility of potential participants having acute serious and/or chronic medical illnesses other than those listed will be evaluated on a case-by-case basis by a study physician, PA-C, or ARNP.

- Use of prazosin or other alpha-1 antagonist (including but not limited to alfuzosin, doxazosin, silodosin, tamsulosin, terazosin) for any purpose in the 2 weeks prior to initial screen (P1) visit and prohibited throughout the study
- Any prior use of prazosin at a dose of more than 4 mg per day
- Allergy or previous adverse reaction to prazosin or other alpha-1 antagonist
- Active psychosis or psychotic disorder, severe depression (as determined per clinician prescriber judgment), severe psychiatric instability or severe situational life crisis (including evidence of being actively suicidal or homicidal).
- Meets Diagnostic and Statistical Manual of Mental Disorders, 5th Edition (DSM-5) criteria for any Substance Use Disorder except caffeine-related disorders, or tobacco-related disorders.
- History of delirium within the prior 3 months, epilepsy, stroke, dementia, psychotic disorder, or bipolar disorder
- Structural brain abnormalities on any prior imaging with associated clinically evident manifestations
- Current participation in transcranial magnetic stimulation studies
- Women of childbearing potential must not be pregnant, planning to become pregnant during the study period, or nursing.
- Participation in a HA support group or other activity such as meditation or yoga intended to mitigate HA or other chronic pain must be stable at least 4 weeks prior to beginning the initial screen (P1) visit and may not be started during the study
- Failure to record HA data for at least 80% of days during the Screening Period
- Not suitable for study per clinician judgement.

#### **Medication-and other Treatment-Related Considerations:**

- The use of HA rescue or symptom-relieving medications will be allowed during the study. This includes triptans, ergotamines, opioids, simple analgesics (e.g. acetaminophen, aspirin, or non-steroidal anti-inflammatories [NSAIDS], and combination analgesics. Their use will be recorded on the concurrent medication CRF during the Preliminary Screening Period (P1) and throughout the remainder of the study. Randomization of participants will be stratified based on whether their use of HA medications meets ICHD-3 beta criteria for overuse of these medications, as described in section 5.5 below.
- Opioid Medications: Use of opioids for treatment of HA or non-HA-related pain or for any other purpose is allowed during the study. Any opioid use would ideally be excluded due to potential confounding effects on interpretation of response to treatment. However, in this population, particularly in Veterans with chronic pain or undergoing minor orthopedic or dental procedures, opioid use is common. Use of opioids, including frequency and dose, will be recorded on the concurrent medication CRF.
- Cannabis: The use of cannabis in any form is not excluded unless its use meets criteria for Cannabis Use Disorder. All use of cannabis will be documented.
- Other Medications: Participants who are using other medications or treatments on a routine basis must be on a stable dose for at least 4 weeks prior to the Preliminary Screening Period (P1), and

must intend to continue the medication at the same regimen for the duration of the trial unless lack of efficacy, safety, or tolerability dictates otherwise. The following medications and treatments are **not** excluded:

- Psychoactive drugs (for example, anticonvulsants, benzodiazepines, antidepressants, sedative/hypnotics),
- Antihypertensive medications (including beta-blockers, calcium channel blockers, angiotensin converting enzyme [ACE] inhibitors, and angiotensin receptor blockers),
- The use of magnesium in any dose that is prescribed for the purpose of HA prevention or treatment. The incidental use of magnesium in multi-vitamins, laxatives, etc. is permissible but must be documented.
- Hormones (for example, testosterone, estrogen, or progesterone) in any form.
- Onabotulinum toxin A and nerve block injections for the purpose of HA prevention is permissible if the treatment response has been stable during the two most recent treatment cycles.
- The "as-needed" (prn) use of any non-exclusionary medications is allowed; however, such use must be discussed with a clinician prescriber and documented.
- The use of butalbital in any form within 4 weeks of beginning the Preliminary Screening Period (P1) through the end of the participant's study involvement is exclusionary.
- Participants who have been taking trazodone will undergo a 2-week washout period before the Preliminary Screening Period (P1 visit). Combining prazosin and trazodone may increase the risk of priapism. We have decided to begin the washout period before the Preliminary Screening Period in order to remove any confounding variables while on the headache log and actigraphy.
- Sildenafil (Viagra), tadalafil (Cialis), vardenafil (Levitra), and avanafil (Stendra) will not be permitted during the study drug dose Titration Period, because of increased risk of hypotension in combination with alpha-1 blockers, but will be allowed at half the usual starting dose following the study drug dose Titration Period, per VA prescribing guidelines.
- Use of supplements containing nitrates and supplements containing stimulants (such as ephedra) are exclusionary in the two weeks prior to initial screen (P1) visit and prohibited throughout the study. Participants who take these supplements will be asked to discontinue them for a minimum of two weeks before the Preliminary Screening Period (P1 visit).
- Use of prescribed stimulants (such as amphetamine or dextroamphetamine containing medications) is exclusionary in the 2 weeks prior to the initial screen (P1) visit and prohibited throughout the study. Participants who take these medications will be asked to discontinue them for a minimum of 2 weeks before the Preliminary Screening Period.
- Participants may also be excluded at the discretion of PI or study clinicians if they appear to be unsuitable for this research study for a reason not detailed here. This may include risk factors for COVID-19 infection that are considered to present excessive risk given background local COVID-19 transmission rates and available safety protocols at the time of evaluation.

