Prazosin should not be taken concurrently with trazodone. Potential participants who are taking trazodone for sleep and who are willing to discontinue will be washed out before starting this study. Care should be taken when alpha-1 blockers are combined with erectile dysfunction medications. We will be following VA pharmacy prescribing guidelines regarding these medications. They will not be allowed during the Titration Period. Once the Stable Dose Period has been reached, erectile dysfunction medications will be allowed at 1/2 the usual clinical dose.

In our current study of prazosin in active duty SMs at Madigan, we have noticed an increased use of dietary supplements containing nitrates. In one case, a participant experienced three episodes of priapism while taking one of these supplements with prazosin. Therefore, use of these supplements and supplements containing stimulants (such as ephedra) will be exclusionary for the duration of the study. Participants who take these supplements will be asked to discontinue them before the Preliminary Screening Period begins.

In post-marketing experience, intraoperative floppy iris syndrome (IFIS) has been observed during cataract surgery in some patients who are taking or have taken alpha-1 blockers. The patient's ophthalmologist should be prepared for possible modifications to the surgical technique to reduce the surgical risk of IFIS. If a patient needs to have cataract surgery, he/she should tell his/her eye surgeon that he/she may have taken prazosin in a research study.

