**Risk Management and Emergency Response:** Evaluation for adverse effects and review of concurrent medications will be completed at all study visits. Participants are asked about suicidal ideation at each in-person visit. If endorsed, participants will be assessed as to their level of risk and the level of care required to keep them or others from harm. If a participant requires inpatient treatment in order to prevent harm or is found to have symptoms of disorganized thought processes secondary to psychosis, mental health personnel will be notified immediately to assist with appropriate triage and referral. Vital signs, including orthostatic blood pressure (BP) and heart rate (HR) will be performed at all study visits. Systolic and diastolic BP and HR will be obtained following 10 minutes of rest, and repeated following 2 minutes of standing. Occurrences of lightheadedness, dizziness on standing, palpitations, drowsiness, nausea, nasal congestion, peripheral edema, worsening of HA, and other adverse effects will be rated by the clinician. For vital signs parameters, unacceptable side effects will include resting hypotension (systolic BP<100 mm Hg) and clinically meaningful hypotension (20 mm Hg or more drop in systolic BP accompanied by dizziness, lightheadedness, or syncope).

For participants taking other antihypertensive medications, their primary care provider will be informed of clinically significant BP reductions at any time during the study, to allow adjustment of the participant's antihypertensive regimen. As a further precaution, male subjects will be advised to sit on the toilet for urination the first two nights to avoid orthostatic hypotension secondary to micturition syncope.

Safety monitoring is based on long-term clinical experience with prazosin. Prazosin was first introduced in 1976 under the trade name Minipress (Pfizer) for clinical management of hypertension, and later became widely prescribed for urinary outflow obstruction secondary to benign prostatic hypertrophy. It has been safely prescribed to large numbers of middle-aged and older people over the past 40 years. The following information regarding the side effect profile and safety record of prazosin is a synopsis from the Minipress package insert: "The most important adverse effect to be considered when prescribing

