After the above procedures are completed, participants will receive the study drug and will be instructed in dosing procedures and safety precautions to prevent potential adverse effects. They will be instructed to continue keeping the daily HA Log, and to start taking the study drug that evening. The prazosin titration schedule is summarized in the Study Drug Titration table. The dosing regimen is based on our experience using prazosin to treat combat-trauma PTSD. The starting dose will be a 1 mg capsule of study drug (prazosin or identical placebo) qhs for the first 2 nights. Then the dose will be increased to 2 mg qhs. For the first week, the study drug will be taken while the participant is in bed for the night, to avoid orthostatic syncope, an uncommon but recognized "first-dose" effect of prazosin. The first-dose effect is avoidable by starting study drug with a low dose, then titrating upward gradually.

The participant will be asked to call the study team the morning after the first dose to make sure there was no occurrence of postural dizziness. The participant will be given a 24-hour contact number in case of adverse events any time the dose is increased.

Dose Titration Visits: Participants will be seen at each dose increase beginning after completion of the first week, according to the titration schedule summarized in the Study Drug Titration Schedule table, to evaluate for adverse effects; record any new medications and interval medical problems; monitor resting and standing BP and HR; confirm that the HA Log is current; determine whether proceeding to the next step of the dose titration is appropriate; and to provide additional study drug for the scheduled dose increase or dose maintenance. A dose increase will occur if the participant does not have unacceptable side effects. Clinical judgement may be used to maintain or decrease the dose as necessary. Dose titration visits are scheduled at the completion of Titration weeks 1 to 5.

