If a participant has intolerable side effects, the dose will be reduced to the previously tolerated titration step. If the participant is unable to tolerate a minimum dose of 1 mg/day, he/she will be terminated from the study. Once the maximum dose has been achieved (5 mg qam and 20 mg qhs or the maximum tolerated dose), the participant will continue on that dose for a total of 12 weeks (Steady-Dose Period), unless he or she develops intolerable medication-related side effects. The dose may be re-challenged during the titration period if clinically appropriate.

|         |                   | Morning (qam) dose | Bedtime (qhs) dose |
|---------|-------------------|--------------------|--------------------|
| Week T1 | Days 1-2          |                    | 1 mg               |
|         | Days 3 -7         |                    | 2 mg               |
| Week T2 | Days 8 -14        | 1 mg               | 4 mg               |
| Week T3 | Days 15 -21       | 2 mg               | 6 mg               |
| Week T4 | Days 22 - 28      | 5 mg               | 10 mg              |
| Week T5 | Days 29 – 36      | 5 mg               | 15 mg              |
| Week T6 | Day 36 + 12 weeks | 5 mg               | 20 mg              |

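### Half-dose erectile-dysfunction drugs become allowed before any scheduled blood pressure at the final prazosin dose, and two sections give different dose limits

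*Combined protocol and SAP*

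**What the plan says.** **The ban and its end.** Section 5.4 (*Medication-and other Treatment-Related Considerations*) names sildenafil, tadalafil, vardenafil and avanafil. They "will not be permitted during the study drug dose Titration Period, because of increased risk of hypotension in combination with alpha-1 blockers", and afterwards they "will be allowed at half the usual starting dose following the study drug dose Titration Period". Section 5.1 (*Foreseeable Risks*) puts it differently: "Once the Stable Dose Period has been reached, erectile dysfunction medications will be allowed at 1/2 the usual clinical dose". It adds: "We will be following VA pharmacy prescribing guidelines regarding these medications". Neither section makes use depend on a blood pressure (BP) reading.

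**The schedule.** The titration table in section 5.5 gives 5 mg in the morning and 20 mg at bedtime for "Day 36 + 12 weeks", in a row labelled Week T6. Once the maximum or maximum tolerated dose is reached, "the participant will continue on that dose for a total of 12 weeks (Steady-Dose Period"). For visits, "Dose titration visits are scheduled at the completion of Titration weeks 1 to 5". The next scheduled visit is SD1, at the end of steady-dose week 1. Visits may move by 6 days either way.

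**The trial's own BP limits.** Section 5.1 (*Risk Management and Emergency Response*) says that "unacceptable side effects will include resting hypotension (systolic BP<100 mm Hg) and clinically meaningful hypotension", the latter being a symptomatic systolic drop of at least 20 mm Hg.

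**The concern.** The reason given for the ban is additive hypotension with an alpha-1 blocker. That reason does not weaken at the last step, when the prazosin dose is highest. Every earlier step on the standard schedule is followed by a resting and standing BP while the ban is still in force. The last step appears to be the exception: the drugs become available before anyone is scheduled to measure BP at the new dose. Section 5.4 also lets participants stay on other antihypertensives.

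Two matters of wording add to this. The end of titration is not sharply defined, so sites may lift the ban on different days. The permitted dose is also stated in two ways, so a participant whose usual dose exceeds the starting dose has two different limits. What is at stake is the safety of a few participants, not the inference.

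**Working it through.** **Inputs (section 5.5 unless noted).** The 20 mg bedtime dose starts on Day 36. Titration visits fall at the end of weeks 1 to 5. SD1 falls at the end of steady-dose week 1. The visit window is plus or minus 6 days. Titration may be extended from 5 to 7 weeks. The trial randomizes 160 participants 2:1 (section 5.1).

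**Step 1: which dose is checked at which visit.** The Schedule of Study Visits numbers Baseline T1 and the visits of weeks 1 to 5 T2 to T6. The T6 visit therefore measures BP on 5 + 15 mg and dispenses 5 + 20 mg. The next scheduled orthostatic BP is at SD1.

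**Step 2: when the ban ends, reading A (five titration weeks).** Section 5.5 speaks of a five-week titration, and the 12 weeks that begin on Day 36 are the Steady-Dose Period.
- The ban ends on Day 36, the day of the increase.
- SD1 = 36 + 7 = Day 43, so the gap is 7 days.
- With the window, the gap is 7 − 6 = 1 to 7 + 6 = 13 days.
- If titration is extended to seven weeks and ends with an increase, the final dose starts on Day 7 × 7 + 1 = 50 and SD1 is Day 57. The gap is again 7 days.

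**Step 3: reading B (Week T6 is a sixth titration week).**
- The ban ends on Day 36 + 7 = 43, so it covers the first week at 20 mg.
- No visit is scheduled at the end of week 6 for someone on schedule, because T7 and T8 are optional visits for delayed titration.
- SD1 = 43 + 7 = Day 50. The ban still lifts 7 days before the first scheduled BP at 20 mg.

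**Step 4: choosing between the readings.** Reading B is supported by the row label, by Day 36 standing in both the Week T5 and Week T6 rows, and by the rule against raising the dose once the Steady-Dose Period has begun. Against it, reading B gives 1 + 12 = 13 weeks at 20 mg, where the text gives 12.

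The stated maximum trial length is reproduced by 4 + 1 + 7 + 12 = 24 weeks. It does not settle the matter, because up to 14 days are allowed before Baseline. Even reading A can then reach 4 + 2 + 7 + 12 = 25 weeks. Reading A is better supported, but not certain.

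**Step 5: size of the last step.**
- Bedtime dose 15 to 20 mg: 20/15 − 1 = +33%.
- Daily dose 20 to 25 mg: 25/20 − 1 = +25%.
- Earlier bedtime steps (1, 2, 4, 6, 10, 15 mg): +100%, +100%, +50%, +67%, +50%. Earlier daily steps (1, 2, 5, 8, 15, 20 mg): +100%, +150%, +60%, +88%, +33%.

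The last step is the smallest in relative terms on both scales.

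**Step 6: who could be affected.** At most 160 × 2/3 ≈ 107 participants take prazosin. That ceiling includes women and participants who never reach 20 mg. The documents give no figure for use of these drugs or for reaching 20 mg on schedule.

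**The case against.** The strongest reply is that the permission is not unconditional. Section 5.4 ties it to VA prescribing guidelines and section 5.1 says they will be followed. They may already require a stable alpha-blocker dose or a BP check. A reader might infer that nothing binding on staff calls for a check; the documents do not support that. They show only that the protocol text states no such condition.

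Other safeguards are real. The dose is halved, and as-needed use must be discussed with a prescriber and documented. The step to 20 mg is taken only after an assessment at 15 mg without unacceptable effects. A 24-hour contact number is given with each increase, and extra safety visits are possible. The package-insert text in section 5.1 says first-dose syncope mostly does not recur in later titration, although that concerns prazosin alone. These points keep the risk small. None is a stated BP check at the final dose.

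It is also fair that a BP taken while the drugs are still banned reflects study drug alone and does not test the combination. That limits what the fix can achieve. It remains a reasonable screen against adding a second hypotensive drug in someone already low. Linking the ban to BP checks is this review's comparison; the protocol does not make it.

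Finally, under reading B the most pointed form of the concern, release on the day of the increase, disappears. What remains is the missing scheduled reading before release.

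**Conclusion.** The point holds as a minor, low-severity safety improvement. For a participant titrated on schedule to 20 mg, the protocol text allows half-dose use nominally 7 days before the first scheduled BP at that dose, with a range of 1 to 13 days on the better-supported reading. On the alternative reading the first week at 20 mg is covered, but the ban still ends without a scheduled reading. A participant held at a dose already checked at a titration visit is not affected. The conflict between half the clinical and half the starting dose holds on either reading.

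A reader might stretch the interval by pairing an early T6 visit with a late SD1 counted from nominal Day 36. That starts the ban on one clock and SD1 on another. With both counted from the same day, 13 days is the maximum. Nor do the documents support inferring a large hazard, since neither the number of users nor the guideline content is given.

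The conclusion assumes that the visit schedule is followed as written and that no unscheduled BP is taken. Power and the primary analysis are unaffected.

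**What to change.** 1. In sections 5.1 and 5.4, allow these drugs only after an acceptable resting and standing BP at the final dose. Take the reading at SD1, or rely on a titration visit if that dose was already checked there. Define acceptable by the section 5.1 limits: no resting systolic BP below 100 mm Hg and no symptomatic systolic drop of 20 mm Hg or more.
2. State one dose limit in both sections: half the usual starting dose.
3. Correct the Week T6 label and the duplicated Day 36 in the titration table, so that the end of titration is unambiguous and the last increase does not fall foul of the bar on later increases.

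The cost is protocol wording and about a week's delay in an optional concomitant drug for a few participants. No visit is added. If SD1 is remote, the home BP cuffs already described in section 5.5 can supply the reading. The check screens for hypotension on study drug only; it does not show that the combination is safe.
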